1 LIST OF ABBREVIATIONS

ACL Anterior Cruciate Ligament ADE Adverse Device Effect

AE Adverse Event

ALT/SGPT Alamine Transaminase/Serum Glutamic Pyruvic Transaminase

ANOVA Analysis of Variance
AP Anterior Posterior
AR Adverse Reaction

AST/SGOT Aspartate Aminotransferase/Serum Glutamic Oxaloacetic Transaminase

AUC Area Under the Curve BMI Body Mass Index

CFR Code of Federal Regulations
CRO Contract Research Organization

CTM Clinical Trial Material
CV Curriculum Vitae
DMP Data Management Plan
eCRF electronic Case Report Form
EDC Electronic Data Capture

ePRO Electronic Patient Reported Outcomes

EQ-5D-5L EuroQoL 5 Dimension

EQ VAS EuroQoL Visual Analog Scale

EULAR European League Against Rheumatism

FDA Food and Drug Administration g, mg, kg gram, milligram, kilogram GCP Good Clinical Practices

GEE Generalized Estimating Equations

h hour(s)

HA Hyaluronan / Sodium Hyaluronate / Hyaluronic Acid

HbA1C Hemoglobin A1C

HIPAA Health Insurance Portability and Accountability Act

IA Intra-articular

ICF Informed Consent Form

ICH International Council for Harmonization

IND Investigational New Drug
INR International Normalized Ratio
IRB Institutional Review Board

ISO International Organization for Standardization

ITT Intent-to-Treat

K-L Kellgren-Lawrence classification

MedDRA Medical Dictionary for Regulatory Activities

MCH Mean Corpuscular Hemoglobin

MCHC Mean Corpuscular Hemoglobin Concentration

MCV Mean Corpuscular Volume mL, mm, m milliliter, millimeter, meter

NSAIDs Non-Steroidal Anti-Inflammatory Drugs

NRS Numerical Rating Scale

OA Osteoarthritis

OARSI Osteoarthritis Research Society International

OMERACT Outcomes Measures for Rheumatic Arthritis Clinical Trials

PA Posterior Anterior PE Physical Exam

PI Principal Investigator

PP Per Protocol
PT Prothrombin Time

PTT Partial Thromboplastin Time

RBC Red Blood Cell ROM Range of Motion

SADE Serious Adverse Device Effect

SAE Serious Adverse Event
SAR Serious Adverse Reaction
SAP Statistical Analysis Plan

SOP Standard Operating Procedure

SUSAR Suspected Unexpected Serious Adverse Reaction

TEAE Treatment Emergent Adverse Events

TH Triamcinolone Hexacetonide

UADE Unanticipated Adverse Device Effect

UK United Kingdom
US United States
VAS Visual Analog Scale
WBC White Blood Cell

WOMAC Western Ontario and McMaster Universities Osteoarthritis Index

2 DEFINITIONS

Baseline: The assessments performed prior to the study injection after the Screening Visit.

Blinded Evaluator: The Blinded Evaluator will be a physician, research nurse, registered physiotherapist or physician assistant trained by the Principal Investigator (PI) to perform the assessments outlined in the protocol. The Blinded Evaluator will complete the Physical Exam, Physical Evaluation of both knees, Range of Motion (ROM) assessment of both knees, and the Evaluator Global Assessment.

End of Study: End of study is defined as the last subject's last visit.

Enrolled: A Subject who has signed the informed consent form (ICF) is enrolled.

Index Knee: The knee that meets the eligibility criteria for treatment. The Index knee may also be termed the "study knee". In subjects with bilateral knee Osteoarthritis (OA), where both knees meet eligibility criteria, the more symptomatic knee is the Index knee.

Institutional Review Board (IRB) refers to an independent body (e.g. Research Ethics Boards, Independent Ethics Committees) whose responsibility is to ensure the protection of rights, safety and well-being of human subjects involved in a trial. Committees with these responsibilities will be referred to in this document as IRB.

Rescue Medication: Acetaminophen will be distributed as the rescue medication. It is the only medication that should be taken for knee pain during the entire study. Rescue medication will be discontinued at least 48 hours prior to Baseline and all follow-up visits.

Treating Physician: The Treating Physician will most often be the PI. He/she will administer the Cingal[®], Triamcinolone Hexacetonide (TH), or Placebo injection but will not participate in the efficacy evaluation.

Treatment Failure: A Subject who undergoes a procedure or uses a medication (other than the rescue medication) for the treatment of OA in the Index knee at any time after the study injection through the 26-week visit.

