9.2.5 Restricted Medications

All analgesics other than acetaminophen are prohibited during the study. This includes, but is not restricted to, NSAIDs, opioids and topical agents for treatment of OA in the Index knee. Topical corticosteroids are allowed at any other site other than the Index knee. The analgesic medication use will be monitored at each Subject visit through review of the Subject Electronic Diary.

The use of IA injection of steroids in any joint and the use of IA injection of viscosupplements in the knee joint is prohibited throughout the study. The use of immunosuppressive agents such as cyclosporine, methotrexate are prohibited throughout the study.

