9.9 Post-Treatment Follow-Up

All study subjects will have follow-up assessments at 1, 3, 6, 12, 18, and 26 weeks after injection day to evaluate effectiveness of the treatment and to assess AEs and protocol compliance. The Blinded Evaluator will evaluate the clinical status of the Subject at each visit.

At least 48 hours prior to the visit, the Subject will be reminded of the visit date and time, the need to abstain from acetaminophen for at least 48 hours prior to each follow-up visit and the requirement to bring their Subject Electronic Diary and the acetaminophen for a pill count with them to the appointment.

If the Subject arrives for a study visit without discontinuing acetaminophen for at least 48 hours prior to the visit, the visit should be rescheduled within the allowed study window. Study assessments should be performed as soon as possible and the protocol deviation, if applicable, recorded in the source and eCRF. The Subject must be re-educated about the importance of protocol compliance.

If the Subject does not come in at the expected time, at least three attempts will be made to contact the Subject in order to accomplish maximum Subject compliance with the follow-up schedule.

The following post-treatment visits will be performed. The Subject will be asked whether any concomitant medications have been taken. All assessments will be done by the Blinded Evaluator.

9.9.1 1 Week ± 3 Days

- Concomitant Medications
- Assess Adverse Events
- Confirm Rescue Medication Washout
- Count/Dispense Rescue Medication Pills (if needed)
- Evaluate Subject Electronic Diary
- Physical Evaluation (Both Knees) to be performed by Blinded Evaluator
- ROM (Index Knee) to be performed by Blinded Evaluator
- Evaluator Global Assessment to be performed by Blinded Evaluator
- WOMAC (Both Knees)
- VAS Pain Scale (Both Knees)
- NRS Pain Scale (Both Knees)
- EuroQoL-5D-5L
- Patient Global Assessment

9.9.2 3 Weeks ± 3 Days

- Concomitant Medications
- Assess Adverse Events

- Confirm Rescue Medication Washout
- Count/Dispense Rescue Medication Pills (if needed)
- Evaluate Subject Electronic Diary
- Physical Evaluation (Both Knees) to be performed by Blinded Evaluator
- Evaluator Global Assessment to be performed by Blinded Evaluator
- ROM (Index Knee) to be performed by Blinded Evaluator
- WOMAC (Both Knees)
- VAS Pain Scale (Both Knees)
- NRS Pain Scale (Both Knees)
- EuroQoL-5D-5L
- Patient Global Assessment

9.9.3 6 Weeks ± 3 Days

- Concomitant Medications

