11.3.1 OMERACT-OARSI responder

The OMERACT-OARSI response rates for the Cingal® arm, TH arm, and the Placebo arm will be calculated for each time point and all pairwise difference confidence intervals will be constructed utilizing the normal approximation to the binomial distribution [29, 30].

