15.9 Protocol Adherence

The Investigator agrees to conduct the study according to the protocol and agrees that all persons delegated to perform study procedures will do so as well. The Investigator must read the protocol thoroughly and must follow the instructions exactly. Investigators shall propose to Anika Therapeutics, Inc. any appropriate modifications to the Protocol or of the use of the CTM. Any change should be agreed to by prior discussion between Anika Therapeutics, Inc. and the Investigator, with written protocol amendments made prior to affecting the changes agreed upon. The Investigator is not to conduct any protocol modifications without prior written permission from Anika Therapeutics, Inc. Investigator will refrain from implementing any modifications to the protocol without agreement from the Sponsor, IRB and FDA, if applicable. Each Investigator will be responsible for enrolling only those subjects who have met protocol eligibility criteria.

Deviations from the protocol include, but are not limited to, the use of prohibited medications or therapies, out of window visits, etc. All protocol deviations should be documented and explained. Major protocol violations are defined as those that could impact the efficacy evaluation such as a Subject is ineligible, missing key data, received an unauthorized treatment, etc. All subjects with protocol deviations will continue to be followed for safety and efficacy assessments. Analysis of study data will be done on both the ITT and PP populations.

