# 4.1.3 Secondary Efficacy Endpoints

4.1.3.1 The responder rate as identified by the Outcomes Measures for Rheumatic Arthritis Clinical Trials-Osteoarthritis Research Society International (OMERACT-OARSI) responder index at 26 weeks post treatment comparing the Cingal® arm to the TH arm, the Cingal arm to the Placebo arm, and the TH arm to the Placebo Arm.

The response rate for the Cingal group and Triamcinolone Hexacetonide (TH) group will be calculated and tested using Fisher's exact test. Formally, the hypothesis to be tested is:

```
H0: \pi_C = \pi_T versus H0: \pi_C \neq \pi_T
```

Where  $\pi_C$  is the responder rate for the Cingal group and  $\pi_T$  is the responder rate for the triamcinolone hexacetonide group.

The response rate for the Cingal Arm, the Placebo Arm and Triamcinolone Hexacetonide (TH) Arm will be calculated and tested using Fisher's exact test. Formally, the hypotheses to be tested are:

```
H0: \pi_C = \pi_P versus H0: \pi_C \neq \pi_P
H0: \pi_T = \pi_P versus H0: \pi_T \neq \pi_P
```

Where  $\pi_C$  is the responder rate for the Cingal Arm,  $\pi_T$  is the responder rate for the triamcinolone hexacetonide Arm, and  $\pi_P$  is the responder rate for the Placebo Arm.

This will be estimated and tested using PROC FREQ with the EXACT option. The results will be displayed similar to:

Summary of the OMERACT-OARSI Responder Rates at 26 Weeks

Parameter	Cingal	Placebo	TH
Estimate n/N (%)			
Cingal vs TH (Primary) (p-value)			
Cingal vs Placebo (p-value)			
Placebo vs TH (p-value)			

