### 4.1.4 Exploratory Endpoints

Any comparisons between groups (Cingal, Placebo, TH), within groups and / or time points (from baseline through to 26 weeks) not described in the primary or secondary endpoints may be presented in the exploratory endpoints including:

- EuroQoL (EQ-5D)
- WOMAC Pain Score (100mm VAS)
- OMERACT-OARSI
- Total WOMAC
- WOMAC Stiffness Score
- WOMAC Physical Function Score
- Patient Global Assessment
- Evaluator Global Assessment
- Range of Motion
- Rescue Medication Usage: Difference in analgesic use measured by number of pills taken between visits will be compared between treatment groups descriptively.
- Number of Subjects Considered Treatment Failures: Treatment Failure: A subject who undergoes a procedure or uses a medication (other than the rescue medication) for the

treatment of OA in the index knee at any time after the study injection through the 12 week visit.

For the exploratory analyses, the continuous variables will be analyzed via an analysis of variance and contrasts used to assess the prescribed comparisons. For the discrete variables, a Fisher's exact test will be used to assess the desired comparisons.

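### A subject who uses a non-rescue medication for OA of the Index knee and stays in follow-up is a Treatment Failure, yet can still be counted as an OMERACT-OARSI responder at week 26

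*Protocol*

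**What the plan says.** **Who is a failure.** Protocol Section 2 covers "A Subject who undergoes a procedure or uses a medication (other than the rescue medication) for the treatment of OA in the Index knee" from the study injection through the 26-week visit, and 11.4 repeats this. SAP 4.1.4 applies the same idea only "at any time after the study injection through the 12 week visit".

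**Which drugs.** Protocol 9.2.5: "All analgesics other than acetaminophen are prohibited during the study". Stable oral glucosamine or chondroitin, if already in use, is permitted (9.2.4).

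**How visit scores are protected.** Under 9.9, if a subject arrives "without discontinuing acetaminophen for at least 48 hours prior to the visit, the visit should be rescheduled within the allowed study window". The Schedule of Events also asks sites to confirm at each visit that other pain medication has been stopped. It attaches no consequence for the scores if it has not.

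**What happens to users.** Protocol 15.9: "Deviations from the protocol include, but are not limited to, the use of prohibited medications or therapies, out of window visits, etc". It then says: "All subjects with protocol deviations will continue to be followed for safety and efficacy assessments". By contrast, 9.9.7 terminates subjects who want further treatment of the Index knee, giving HA and steroid injections as examples, and 15.20 lists treatment failure among example reasons for withdrawal.

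**How response is analysed.** Under protocol 11.3.1 the response rates "will be calculated for each time point and all pairwise difference confidence intervals" are constructed. SAP 4.1.3.1: "The response rate for the Cingal group and Triamcinolone Hexacetonide (TH) group will be calculated and tested using Fisher's exact test", with parallel tests against Placebo. Neither section mentions Treatment Failure. Primary and secondary endpoints use the ITT population, and multiple imputation fills in missing values only (protocol 11.8, SAP 4.5).

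**The concern.** The study objective is the size and duration of relief from the injection itself. The acetaminophen washout shows that the plan does not want another analgesic to colour the visit scores. For the remaining analgesics the plan stops at prohibition. A subject who starts a daily NSAID for the Index knee at week 10, stays in the study and feels better at week 26 has, by the protocol's own definition, failed the injection, and can still count as a success of it in the first-listed secondary endpoint.

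This can overstate responder rates in any arm. If subjects whose injection has worn off reach for other drugs more often, the overstatement is larger in the weaker arm and the between-arm difference is understated.

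**Working it through.** **Does the text allow it?**

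1. Non-rescue medication for OA of the Index knee makes the subject a Treatment Failure (protocol 2, 11.4).
2. The same use is a protocol deviation, and subjects with deviations continue efficacy assessments (15.9). A week-26 score on the other drug can therefore exist.
3. An observed score is not missing, so imputation does not touch it (11.8, SAP 4.5).
4. No sentence in 11.3.1 or SAP 4.1.3.1 overrides the resulting classification. Treatment Failure appears only among exploratory endpoints (protocol 6.3, 11.4; SAP 3.3, 4.1.4).

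No passage says in words that such scores are used as observed. That follows from steps 2 to 4 together.

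**The plan's own figures.** The only power statement concerns mean WOMAC pain. With 99 per arm and SD 20, the standard error is 20 × √(2/99) = 2.84. For 8 points, 8/2.84 = 2.81 and power is Φ(2.81 − 1.96) = 80.4%. For 10 points it is 94.0%. Both statements reproduce. The plan gives no responder rate and no Treatment Failure rate, so the rest is illustration.

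**Size of the shift.** Let f be the proportion of an arm who are failures and remain in follow-up, and r the proportion of those who meet the response criteria on the other drug (assumed 0.5). An arm's rate is raised by r × f. Relative to counting failures as non-responders, the Cingal − TH difference shrinks by r × (f_TH − f_Cingal).

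| f Cingal | f TH | Cingal raised by | TH raised by | Difference shrinks by |
|---|---|---|---|---|
| 5% | 5% | 2.5 points | 2.5 points | 0 |
| 5% | 10% | 2.5 points | 5.0 points | 2.5 points |
| 5% | 15% | 2.5 points | 7.5 points | 5.0 points |

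As head counts, 99 × 0.05 × 0.5 ≈ 2.5 subjects on Cingal, and 99 × 0.10 × 0.5 ≈ 5 to 99 × 0.15 × 0.5 ≈ 7.4 on TH. With r from 0.3 to 0.7, the last two rows give 0.3 × 5 = 1.5 up to 0.7 × 10 = 7.0 points.

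**Worked example.** Assume 70% (Cingal) and 60% (TH) respond among non-users, with f of 5% and 10%.

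- Failures as non-responders: 0.70 × 0.95 = 66.5% and 0.60 × 0.90 = 54.0%, a difference of 12.5 points.
- As observed: 66.5 + 2.5 = 69.0% and 54.0 + 5.0 = 59.0%, a difference of 10.0 points.

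The 95% half-width for the as-observed difference is 1.96 × √((0.69 × 0.31 + 0.59 × 0.41)/99) = 13.3 points.

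**If some failures leave.** Should half of the failures leave in each arm, f halves and the shift becomes 1.25 to 2.5 points. Those who leave have no week-26 score and fall to imputation, which is a different question.

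**The case against.** Five points can fairly be made against this.

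- **Failures may leave.** Section 9.9.7 is open-ended in the treatments it covers, and 15.20 names treatment failure as a reason for withdrawal. A reader might infer that every Treatment Failure is carried to week 26 and risks being called a responder. The documents do not support that. Nor do they say that all leave, because 15.9 keeps subjects with deviations in follow-up and 15.20 gives examples only. The point applies to those who remain, whose number is unknown.
- **Per Protocol analysis.** Receipt of an unauthorized treatment is already an example of a major violation in 15.9, and major violators are excluded from the PP population. This stands in large part. However, prohibited-medication use is also listed among ordinary deviations, and the PP analysis is secondary.
- **It is an estimand choice.** Using scores regardless of other medication is a legitimate treatment-policy reading of ITT, and the protocol calls this a pilot without formal testing. For mean WOMAC pain that carries weight: the same scores enter there, but nobody is labelled a success. A reader might infer that the primary analysis is therefore wrong, which does not follow. The contradiction is specific to the responder endpoint, where one subject can hold opposite labels. Bias also matters for estimation, and the SAP does test responder rates.
- **Bluntness.** A failure-as-non-responder rule catches a single early use that is irrelevant by week 26. This stands, and it is the reason to keep an as-observed sensitivity analysis.
- **Size.** The figures rest wholly on assumptions, and shifts of 2.5 to 5 points are well inside a half-width of about 13. Both statements are correct. The response criteria themselves are cited but not reproduced in the documents, so the assumed r cannot be checked.

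**Conclusion.** The gap is real and limited. Followed as written, the plan can count a protocol-defined Treatment Failure who remains in follow-up as a week-26 OMERACT-OARSI responder. Responder rates are then overstated by r × f in each arm. The Cingal − TH difference shrinks by about 2.5 to 5 points if 5% versus 10% to 15% are failures who remain and half respond on the other drug. It shrinks less if some leave and is unaffected if use is equal.

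A reader might infer that the comparison is certainly biased toward zero. The documents give no rate of use by arm, so more use in the weaker arm is plausible but not established. If use were more common on Cingal, the shift would go the other way.

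The SAP's 12-week window is a separate, plain conflict with the protocol's 26 weeks. Under the SAP wording a subject who starts another drug in week 14 is not even in the exploratory count.

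**What to change.** 1. In SAP 4.1.3.1 and protocol 11.3.1, add: *A subject who has met the Treatment Failure definition by a visit is counted as a non-responder at that visit. Stable glucosamine or chondroitin use permitted under 9.2.4 does not count.* Report the as-observed responder rate as a sensitivity analysis, so that the effect of an isolated early use is visible.
2. Change the Treatment Failure window in SAP 4.1.4 from 12 to 26 weeks to match protocol 2 and 11.4. Otherwise the new rule misses failures after week 12.
3. Reconcile protocol 9.9.7, 15.9 and 15.20 on whether Treatment Failures leave the study or continue in follow-up.
4. As a clarification only, state in the PP definition whether use of a prohibited analgesic is an unauthorized treatment and hence a major violation.

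**Cost.** Wording in two documents. Medication name, indication and start and stop dates are already collected (protocol 9.2.6), so failure by medication can be derived. The documents do not show a ready-made flag. Responder rates will be somewhat lower in any arm with such use, and a subject with one brief early use will be a non-responder in the main responder analysis.

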3 STUDY SYNOPSIS

	TABLE TO THE PROPERTY OF THE P							
Title	A Randomized, Double-Blind, Placebo Controlled, Multi-Center Study of a Single							
	Injection Cross-Linked Sodium Hyaluronate Combined with Triamcinolone Hexacetonide							
Study	(Cingal®) to Provide Symptomatic Relief of Osteoarthritis of the Knee To determine the contribution of Triamcinolone Hexacetonide (TH) to pain relief, both in							
Objective	terms of magnitude and duration, when used within a single injection of Cingal®							
Objective	compared to a single injection of TH in subjects with OA of the knee. A saline placebo is							
	included within the trial to set the expectation of a return to Baseline pain for the							
	Subjects.							
Investigational	Cingal®: A chemically cross-linked sodium hyaluronate supplied as a 4-mL unit dose							
Product	with a nominal 18 mg of Triamcinolone Hexacetonide (TH) in a 5-mL glass syringe.							
Comparator	Triamcinolone Hexacetonide (TH): 20 mg/ml supplied as 1 mL unit dose in a glass							
Products	ampoule.							
	Placebo: 0.9% saline supplied as a 4-mL unit dose in a 5-mL glass syringe.							
Mode of	Cingal®, Triamcinolone Hexacetonide, or Placebo will be injected into the intra-articular							
Delivery	(IA) space of the Index knee using an 18-21 gauge needle.							
Study Design	Multi-center, randomized, double-blind, parallel group, 3-arm, placebo controlled study							
Phase	Pilot Study							
Sample Size	A total of 231 subjects will be enrolled and treated.							
Study Duration	The entire study duration from first Subject in to last Subject out will be 12-16 months.							
	The enrollment phase will be approximately 7-9 months with a follow-up phase of 6							
	months. Visits will be scheduled at Screening, Baseline, 1 week, 3 weeks, 6 weeks, 12							
Inclusion	weeks, 18 weeks and 26 weeks post treatment.							
Criteria	Screening Inclusion Criteria 1. Subject is 40-75 years old.							
Cilteria	2. Body Mass Index (BMI) ≤ 40 kg/m².							
	3. Subject has Kellgren-Lawrence (K-L) severity grade II or III in the Index knee as							
	determined by X-Ray. Contralateral knee: K-L severity grade 0, I or II.							
	4. Subject has had at least two signs and at least two symptoms of OA disease (based							
	on the European League Against Rheumatism (EULAR) recommendations for							
	diagnosing knee OA) in the Index knee for at least 6 months despite conservative							
	treatment (weight reduction, physical therapy, pain medications, etc.). The EULAR							
	signs and symptoms are as follows:							
	Signs: crepitus, restricted movement and bony enlargement							
	 Symptoms: persistent knee pain, limited morning stiffness and reduced function Subject must be willing to abstain from other IA treatments of the knee for the 							
	duration of the study.							
	6. Subject is willing to discontinue all analgesics including nonsteroidal anti-							
	inflammatory drugs (NSAIDs), except acetaminophen before the treatment injection							
	and through the completion of the study. NSAIDs should be discontinued through the							
	Screening period.							
	7. Subject is willing to use only acetaminophen (up to a maximum of 3.0 grams per							
	day) for the treatment of joint pain for the duration of the study. At least forty-eight							
	hours prior to the Baseline Visit and each follow-up visit, the Subject is willing to							
	discontinue use of acetaminophen							
	8. Subject is willing to maintain a stable dose of oral glucosamine and/or chondroitin							
	sulfate products throughout the study, if taken prior to signing ICF. 9. Subject is able to understand and comply with the requirements of the study and							
	voluntarily provides consent.							
Exclusion	Screening Exclusion Criteria							
Criteria	Subject received an IA injection of Hyaluronic Acid (HA) and/or steroid in either							
	knee within 6 months of signing the ICF. A Subject will be excluded if they are							
	planning to receive an HA or steroid injection (other than the study injection) in							
	either knee during the course of this study.							
	Subject had an arthroscopy of either knee within 3 months of signing the ICF.							

- 3. Subject had an open surgical procedure of either knee or hip or any surgery of the spine within 12 months of signing ICF. Subject plans to have knee, hip or spine surgery within the study period.
- 4. Subject has intra-articular trauma to the Index knee. Subject has concurrent multisystem or multi-limb trauma.
- 5. Subject has evidence or medical history of the following diseases in the Index knee: septic arthritis; inflammatory joint disease; history of Reiter's syndrome; gout; chondrocalcinosis associated with recurrent episodes of acute synovitis of the knee consistent with pseudogout; osteochondritis dissecans, Paget disease of the bone; ochronosis; acromegaly; hemochromatosis; primary osteochondromatosis; known history of Wilson disease; heritable disorders or collagen gene mutations.
- 6. Subject has a history of cartilage repair surgery in the Index knee within 3 years of signing the ICF.
- 7. Subject has a history of Anterior cruciate ligament (ACL) repair, reconstruction or injury in the Index knee within 3 years of signing the ICF.
- 8. Subject has X-Ray findings of acute fractures, severe bone loss, avascular necrosis, severe bone or joint deformity in the Index knee.
- Subject has significant varus or valgus deformity greater than 8 degrees in either knee.
- 10. Subject has a clinically apparent tense effusion of the Index knee.
- 11. Subject has knee instability in either knee per the Investigator's assessment.
- 12. Subject requires consistent use of an assistive device (e.g. wheelchair, walker, etc.) Occasional use of a cane is acceptable.
- 13. Subject has medical condition(s) which could affect study assessments or may adversely affect the safety and/or success of the study treatment. This includes but is not limited to the following: a. Peripheral neuropathy severe enough to interfere with evaluation of the subject, b. Vascular insufficiency severe enough to interfere with evaluation of the subject, c. Active fibromyalgia, d. Hemiparesis involving either lower extremity, e. Immunocompromised or immunosuppressive disorder or receiving medications to treat immunosuppressive disorders, f. Systemic bleeding disorder(s), g. Current malignancy or treatment within the last 5 years, except for non-melanoma skin cancer, h. Significant psychiatric disorder, i. Active drug and/or alcohol abuse within the past year, j. Uncontrolled diabetes with a Screening Hemoglobin A1C (HbA1c) of >7% k. contraindication to Triamcinolone Hexacetonide (TH) including active tuberculosis, herpes simplex keratitis, acute psychoses and systemic mycoses and paracitoses.
- 14. Subject is taking medications at the time the subjects signs the ICF which could interfere with the treatment procedure, healing and/or assessments. This includes but is not limited to oral or injectable anticoagulant treatments, anti-aggregant platelet treatment, chronic opioid analgesics. Low dose aspirin used for cardiovascular protection is allowed if a stable regimen is maintained for the duration of the study.
- 15. Subject is receiving treatment using electromagnetic stimulation and/or low intensity ultrasound in the Index knee at the time of signing the ICF, within 3 months of signing the ICF or plans to receive treatment any time during the study period.
- 16. Subjects who had an oral, intramuscular, intravenous, rectal suppository or topical (excluded in Index knee only) corticosteroid within 30 days of signing the ICF are excluded. Topical corticosteroid use at any site other than the Index knee is allowed.
- 17. Subject has a pre-treatment contraindication to IA injections or aspiration of the Index knee, including cutaneous infection in the injection site area, active IA infection (as suggested by moderate or marked effusion), knee deformity or condition which, in the opinion of the Investigator could jeopardize the sterility or delivery of the IA injection.
- 18. Subjects with a history of hypersensitivity to any of the ingredients in the

- hyaluronan or previous hypersensitivity to the administration of corticosteroids or an inability to tolerate acetaminophen.
- 19. Subject has any contraindication to the receipt of a corticosteroid.
- 20. Subject is receiving or in litigation for worker's compensation.
- 21. Subject is a woman who is pregnant or breastfeeding at the Screening Visit or a woman of child bearing potential who refuses to use effective contraception during the course of the study.
- 22. Subject was involved in any other research study involving an investigational product, or a new application of an approved product, within 60 days of signing the ICF.
- 23. Subject previously treated with Cingal for knee osteoarthritis.

Baseline Inclusion Criteria

24. Subject has a Western Ontario and McMaster Universities Osteoarthritis Index (WOMAC) pain-sub-score ≥ 50 mm and ≤ 90 mm in the affected knee and ≤ 30 mm in the contralateral knee on a 100 mm Visual Analog Scale (VAS) scale.

Baseline Exclusion Criteria

- 25. Subject has a decrease of ≥ 20 mm in the WOMAC pain-sub-score (average of 5 pain scales) from Screening to Baseline in the Index knee on a 100 mm Visual Analog Scale (VAS) scale.
- 26. Subject has a synovial fluid aspirate volume > 10 mL in the Index knee.
- 27. Subject has a contraindication to continue with the study treatment injection based on the visual appearance of the synovial fluid aspirate unless the fluid is examined microscopically prior to injection with no clinically significant findings (e.g. bacteria, crystals or blood).
- 28. Subject has range of motion of less than 100° flexion in either knee.

Criteria for Evaluation

Efficacy:

Primary Endpoint:

 The change from Baseline in knee pain as measured by the WOMAC Pain Score (100 mm VAS) at 26 weeks post treatment comparing the Cingal® arm to the TH arm, the Cingal arm to the Placebo arm, and the TH arm to the Placebo arm.

Secondary Endpoints:

- The responder rate as identified by the Outcomes Measures for Rheumatic Arthritis Clinical Trials-Osteoarthritis Research Society International (OMERACT-OARSI) responder index at 26 weeks post treatment comparing the Cingal® arm to the TH arm, the Cingal arm to the Placebo arm, and the TH arm to the Placebo arm.
- The change from Baseline in knee pain as measured by daily VAS Pain Score and average weekly VAS Pain Score (100 mm VAS) through 26 weeks post treatment comparing the Cingal® arm to the TH arm, the Cingal arm to the Placebo arm, and the TH arm to the Placebo arm.
- The change from Baseline in knee pain as measured by daily NRS Pain Score and average weekly NRS Pain Score (0-10 NRS) through 26 weeks post treatment comparing the Cingal® arm to the TH arm, the Cingal arm to the Placebo arm, and the TH arm to the Placebo arm.
- The change from Baseline in WOMAC Physical Function score at 26 weeks post treatment comparing the Cingal® arm to the TH arm, the Cingal arm to the Placebo arm, and the TH arm to the Placebo arm.
- The change from Baseline in WOMAC Stiffness score at 26 weeks post treatment comparing the Cingal® arm to the TH arm, the Cingal arm to the Placebo arm, and the TH arm to the Placebo arm.
- The change from Baseline in Total WOMAC score at 26 weeks post

treatment comparing the Cingal® arm to the TH arm, the Cingal arm to the Placebo arm, and the TH arm to the Placebo arm. The change from Baseline in the Patient Global Assessment at 26 weeks post treatment in the Cingal® arm compared to the TH arm, the Cingal arm to the Placebo arm, and the TH arm to the Placebo arm. The change from Baseline in the Evaluator Global Assessment at 26 weeks post treatment in the Cingal® arm compared to the TH arm, the Cingal arm to the Placebo arm, and the TH arm to the Placebo arm. The usage of Rescue Medication through 26 weeks post treatment in the Cingal® arm compared to the TH arm, the Cingal arm to the Placebo arm, and the TH arm to the Placebo arm. **Exploratory Endpoints:** Any comparisons between arms (Cingal®, TH, Placebo), within arms and / or time points (from Baseline through to 26 weeks) not described in the primary or secondary endpoints may be presented in the exploratory endpoints including: EuroQoL (EQ-5D-5L) WOMAC Pain Score (100mm VAS) Daily & weekly VAS pain scores Daily & weekly Numerical Rating Scale (NRS) pain scores OMERACT-OARSI **Total WOMAC** WOMAC Stiffness Score WOMAC Physical Function Score Patient Global Assessment **Evaluator Global Assessment** Range of Motion Rescue Medication Use Number of Treatment Failures Safety: The incidence, timing, severity, and relationship to treatment of all Adverse Events (AE) will be collected and coded using Medical Dictionary for Regulatory Activities (MedDRA). Local injection site and non-local events will be recorded separately. **Statistical** The primary analysis on the endpoints will be performed on the ITT (Intent to Treat) **Analysis** populations using the Multiple Imputation Methodology. The Multiple Imputation Methodology will use a mixed effects repeated measures model to predict the missing values. All Primary and Secondary endpoints will be analyzed using the ITT population. A secondary analysis will be conducted on the Per Protocol (PP) population. Since the primary endpoint is at 26 weeks, this is all subjects who complete the 26 week visit and who are not major violators of the protocol. For all other visits, this is defined as the subjects who complete those visits according to the protocol. All safety analyses will be conducted on all subjects who undergo treatment in any arm. Sites Up to 40 clinical sites in US only **Sponsor** Anika Therapeutics, Inc. [name], United States of America Phone: + 1 [contact] Fax: + 1 [contact]
